8.13.5 Visits at the Study Site, At Home, or Alternate Study Site

Every attempt should be made to assess the participant at the study site for all scheduled study visits and for any unscheduled or post-surgery follow-up visits (see Section 1.3). However, if this is not possible, additional efforts should be made to ensure the per-protocol assessments are conducted for these visits.

A visit at the study site is required for the Day 1 and Day 28 visits in RSV Season 1 to maintain blinding. Study site visits are preferred for all scheduled in-person postdose follow-up visits to ensure the participants are seen in person by the investigator and site staff in the event respiratory infection symptoms or a suspected AESI are present. See Section 1.3 for the visit schedules.

If circumstances do not support a visit at the study site, a home visit by the site personnel or a healthcare service provider (eg, home healthcare vendor) or a visit to an alternate study site location may be appropriate to perform study assessments and procedures per the SoA, where available and when permitted by local regulations and IRB/IEC. All indicated study procedures should be completed, including blood draws. The documentation from the visit should be provided to the investigator or medically qualified designee (consistent with local requirements) for review and assessment per institutional standard. Also, this documentation should be provided to site staff for data entry purposes.

Refer to the home visit manual (or equivalent) for details.

8.13.6 Discontinued Participants Continuing to be Monitored in the Study

In this study, a participant may discontinue from study intervention but continue to participate in subsequent protocol visits as outlined in Section 1.3, as long as the participant's legally acceptable representative does not withdraw consent. Protocol-specified activities should occur at these visits.

9 STATISTICAL ANALYSIS PLAN

This section outlines the statistical analysis strategy and procedures for the study. If, after the study has begun, but prior to any unblinding/final database lock, changes are made to primary and/or key secondary hypotheses, or the statistical methods related to those hypotheses, then the protocol will be amended (consistent with ICH Guideline E-9). Changes to tertiary or other nonconfirmatory analyses made after the protocol has been finalized, but prior to unblinding/final database lock, will be documented in an sSAP and referenced in the CSR for the study. Post hoc tertiary analyses will be clearly identified in the CSR.

9.1 Statistical Analysis Plan Summary

Key elements of the statistical analysis plan are summarized below; the comprehensive plan is provided in Section 9.2 through Section 9.12.

Study Design Overview	A Phase 3, Multicenter, Randomized, Partially Blinded, Palivizumab-Controlled Study to Evaluate the Safety, Efficacy, and Pharmacokinetics of MK-1654 in Infants and Children at Increased Risk for Severe RSV Disease
Treatment Assignment	A total of 1000 participants will be randomized in a 1:1 ratio to the MK-1654 or palivizumab groups on Day 1 (double-blind) in RSV Season 1. All participants who continue into RSV Season 2 will receive 1 dose of MK-1654.
Analysis Populations	Efficacy: Full Analysis Set (FAS) and Per-Protocol Efficacy (PPE) Safety: All Participants as Treated (APaT) Pharmacokinetic: Per-Protocol (PP)
Primary Endpoint(s)	Safety 
 Number of participants with solicited injection-site AEs from Days 1 through 5 after each dose in RSV Season 1. Number of participants with fever as measured by solicited daily body temperatures from Days 1 through 5 after each dose in RSV Season 1. Number of participants with solicited systemic AEs from Days 1 through 5 after each dose in RSV Season 1. Number of participants with anaphylaxis/hypersensitivity AESI from Days 1 through 28 after Dose 1 and Days 1 through 14 after Dose 2 in RSV Season 1. Number of participants with rash AESI from Days 1 through 28 after Dose 1 and Days 1 through 14 after Dose 2 in RSV Season 1. Number of participants with nonserious AEs from Days 1 through 28 after Dose 1 and 14 days after each subsequent dose in RSV Season 1. Number of participants with SAEs through the duration of study participation in RSV Season 1.


Key Secondary Endpoints
	
Efficacy
 
 • Number of participants with RSV-associated MALRI occurring from Days 1 through 150 post Dose 1 in RSV Season 1. • Number of participants with RSV-associated hospitalization occurring from Days 1 through 150 post Dose 1 in RSV Season 1. 
Safety
 
 • Number of participants with solicited injection-site AEs from Days 1 through 5 postdose in RSV Season 2. • Number of participants with fever as measured by solicited daily body temperatures from Days 1 through 5 postdose in RSV Season 2. • Number of participants with solicited systemic AEs from Days 1 through 5 postdose in RSV Season 2. • Number of participants with anaphylaxis/hypersensitivity AESI from Days 1 through 42 postdose in RSV Season 2. • Number of participants with rash AESI from Days 1 through 42 postdose in RSV Season 2. • Number of participants with nonserious AEs from Days 1 through 42 postdose in RSV Season 2. • Number of participants with SAEs from Days 1 through 180 postdose in RSV Season 2. 
Pharmacokinetic
 
 • MK-1654 PK concentration in RSV Seasons 1 and 2.

Statistical Methods for Key Efficacy / Pharmacokinetic Analyses
	
Efficacy
 
The efficacy of MK-1654 compared to palivizumab with respect to the RSV-associated MALRI endpoint in RSV Season 1 will be estimated and the 95% CI of efficacy will be obtained based on the modified Poisson regression with robust variance method proposed by Zou [Zou, G. 2004]. The incidence of RSV-associated hospitalization in the MK-1654 and palivizumab groups in RSV Season 1 will be estimated and the exact 95% CIs will be provided using the Chi-square distribution for Poisson variable method.
 
Pharmacokinetic
 
Population PK modeling will be used to estimate PK parameters for each participant (eg, $AUC_{0-\infty}$, C_{max}, T_{max}, $t_{1/2}$), which will be summarized in a separate population PK modeling report. Additionally, individual concentration values for each PK sample collected will be summarized by timepoint.


Statistical Methods for Key Safety Analyses
	
There are no a priori clinical events identified in this study as Tier 1 events. Tier 2 events identified in this study include solicited injection-site AEs, fever as measured by solicited daily body temperatures, solicited systemic AEs, drug-related AEs, any SAEs, discontinuations due to AEs, anaphylaxis/hypersensitivity AESI, rash AESI, nonserious AEs, and AEs by SOC observed in $\geq 1\%$ of participants in at least 1 group. Estimates and 95% CIs for between-treatment differences in the percentage of participants with events will be calculated using the unstratified Miettinen and Nurminen method [Miettinen, O. and Nurminen, M. 1985].

Interim Analyses	An IA will occur after the first 30 participants are randomized or after the first hemisphere enrollment (~17 weeks) is complete in the initial RSV season of the study, whichever occurs first. Safety follow-up data for these participants through the RSV Season 1 Day 42 phone call will be included in this IA. Summaries of the safety, available PK data, and available incidence of RSV-associated MALRI and RSV-associated hospitalization will be reviewed by the eDMC and a recommendation on whether the study should continue will be made by the eDMC. Details are provided in Section 9.7.
Multiplicity	No multiplicity adjustment is planned as there is no hypothesis testing in this study.
Sample Size and Power	A total of 1000 participants will be randomized in a 1:1 ratio to receive either MK-1654 or palivizumab in RSV Season 1. Section 9.9.2 provides information about the precision of this study to estimate the incidence of AEs.

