6.3 Measures to Minimize Bias: Randomization and Blinding

6.3.1 Intervention Assignment

Intervention randomization will occur centrally using an IRT system. There are 2 study intervention arms. Participants will be assigned randomly in a 1:1 ratio to MK-1654 or palivizumab.

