6.3.2 Stratification

Intervention randomization will be stratified according to the following factors:

1. Region

- Northern Hemisphere
- Southern Hemisphere

2. Participant condition:

- CLD (≥ 200 infants)
- CHD (≥ 100 infants)
- Neither CLD nor CHD < 29 weeks gestational age
- Neither CLD nor CHD ≥ 29 weeks gestational age

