9.6.1 Statistical Methods for Efficacy Analyses

To estimate the efficacy of MK-1654 compared to palivizumab against RSV-associated MALRI through Day 150 post Dose 1 in RSV Season 1, efficacy is defined as:

$$E\% = 100 * \{1 - (R_t/R_p)\}$$

Where R_t and R_p are the incidence rates of RSV-associated MALRI in the MK-1654 and palivizumab groups, respectively. The incidence rate R_t is defined as $R_t = C_t/T_t$, where C_t = the count of RSV-associated MALRI cases in the MK-1654 group and T_t = total person-time of follow-up for efficacy in the MK-1654 group. The incidence rate R_p is defined similarly.

A modified Poisson regression approach with robust variance [Zou, G. 2004] will be used for the efficacy analyses. The mean and 95% CI of relative risk, R_t/R_p , will be obtained from the model, and will be used to estimate the mean and 95% CI of E. The modified Poisson regression model will include treatment group, and stratification variables of region (Southern Hemisphere and Northern Hemisphere) and participant condition (CLD, CHD, neither CLD nor CHD ≥ 29 weeks gestational age, and neither CLD nor CHD < 29 weeks gestational age) as covariates. If the number of participants in any stratum is too small and/or convergence cannot be achieved, the covariate may be excluded from the model. To allow for differences in follow-up times among the participants, the log of the follow-up time as the offset term will be added in the modified Poisson regression.

The incidence of RSV-associated hospitalization occurring from Days 1 through 150 post Dose 1 in the MK-1654 and palivizumab groups in RSV Season 1 will be estimated and the exact 95% CIs will be provided using the Chi-square distribution for Poisson variable method [Ulm, K. 1990].

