9.6.2 Statistical Methods for Safety Analyses

Safety and tolerability will be assessed by clinical review of all relevant parameters including AEs. All safety summaries will be provided separately for the participants' first and second

RSV seasons. Comparisons between the 2 groups will be made in RSV Season 1 only. The primary comparison of safety endpoints in RSV Season 1 will be after the first 2 doses in each group, ie, after the MK-1654 and placebo doses versus after the first 2 palivizumab doses. A supplemental comparison of safety endpoints in RSV Season 1 will be after the MK-1654 and placebo doses versus after all doses in the palivizumab group.

The analysis of safety results will follow a tiered approach (Table 7). The tiers differ with respect to the analyses that will be performed. AEs (specific terms as well as SOC terms) and events that meet PDLCS in laboratory and vital signs parameters are either prespecified as “Tier 1” endpoints or will be classified as belonging to “Tier 2” or “Tier 3” based on the observed proportions of participants with an event.

Tier 1 Events

Safety parameters or AEs of particular interest that are identified a priori constitute “Tier 1” safety endpoints that will be subject to inferential testing for statistical significance. There are no Tier 1 events for this protocol as no treatment-related SAEs have been observed in the Phase 1 studies of MK-1654.

Tier 2 Events

Tier 2 parameters will be assessed via point estimates with 95% CIs provided for differences in the proportion of participants with events (via the unstratified Miettinen and Nurminen method [1985]).

Membership in Tier 2 requires that at least 1% of the participants in any treatment group have the event. All other AEs will belong to Tier 3. Maximum body temperature will be summarized using Brighton Collaboration cutoffs.

The threshold of at least 1% was chosen to draw clinical meaningful inference. When less than 1% of participants report AEs in both groups, the 95% CI for the between-group difference may exclude zero. However, the clinical significance of these differences is unknown given the small number of participants who report AEs. Because many 95% CIs for Tier 2 events may be provided without adjustment for multiplicity, the CIs should be regarded as a helpful descriptive measure to be used in review, not a formal method for assessing the statistical significance of the between-group differences in AEs.

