9.9.2 Sample Size and Power for Safety Analyses

A total of 1000 participants will be randomized in a 1:1 ratio to receive either MK-1654 and placebo or palivizumab in RSV Season 1. The probability of observing at least 1 SAE in this study depends on the number of participants dosed and the underlying percentage of participants with a SAE in the study population. Calculations below assume that 100% of the randomized participants will be evaluable for safety analyses. There is an 80% chance of observing at least 1 SAE among 500 participants in the MK-1654 group if the underlying incidence of a SAE is 0.33% (1 of every 303 participants receiving MK-1654). There is a 50% chance of observing at least 1 SAE among 500 participants in the MK-1654 group if the underlying incidence of a SAE is 0.14% (1 of every 714 participants receiving MK-1654). If no SAEs are observed among the 500 participants in the MK-1654 group, this study will provide 97.5% confidence that the underlying percentage of participants with a SAE is <0.74% (1 in every 136 participants in the MK-1654 group).

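### The primary safety comparison ignores the randomization strata; a stratified interval for the common AE categories would be a cheap, optional gain in precision if AE risk differs between strata

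*Combined protocol and SAP*

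**What the plan says.** Section 6.3.2 states: "Intervention randomization will be stratified according to the following factors". The factors are region (two hemispheres) and participant condition (CLD; CHD; neither, below 29 weeks; neither, 29 weeks or more), which makes eight cells. Minimum sizes are given only for CLD (200) and CHD (100). Section 9.9.2 sets the size: "A total of 1000 participants will be randomized in a 1:1 ratio to receive either MK-1654 and placebo or palivizumab in RSV Season 1".

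For the secondary efficacy endpoint, Section 9.6.1 says "The modified Poisson regression model will include treatment group, and stratification variables of region", and it goes on to include participant condition. A covariate may be left out when a stratum is too small or the model does not converge.

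For safety, the primary objective in Section 3, both places that state the method specify the unstratified interval. Section 9.1 reads "Estimates and 95% CIs for between-treatment differences in the percentage of participants with events will be calculated using the unstratified Miettinen and Nurminen method". Section 9.6.2 says that Tier 2 differences are estimated "via the unstratified Miettinen and Nurminen method". Neither gives a reason. Section 9.6.2 also describes these intervals as descriptive and without multiplicity adjustment, and Section 9.3 says that there is no formal hypothesis testing. Section 9.10 plans subgroup analyses by the same two factors for selected safety endpoints.

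**The concern.** In an estimation study the between-group difference and its interval are the main comparative result for the primary objective. When allocation is balanced within strata, differences in risk between strata do not add to the error of the treatment comparison. An unstratified interval counts them as error all the same. If risk differs between strata, the interval is then wider than it needs to be and covers more than its nominal 95%.

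Such differences are plausible here. The enrolment minimums make the sample a planned mixture of CLD, CHD and preterm infants. SAEs are counted through all of Season 1 participation (Section 9.4.2). Nearly any inpatient admission qualifies as an SAE (Section 10.3.3), and no disease-related events are set aside (Section 8.4.6). The sponsor already treats the two factors as prognostic in the efficacy model. At stake is some precision on the common primary endpoints. Validity is not at stake.

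**Working it through.** **The plan's own safety figures.** Section 9.9.2 uses 500 infants in the MK-1654 group.
- Chance of at least one SAE at 0.33%: 1 − (1 − 0.0033)^500 = 80.8% (stated 80%).
- At 0.14%: 1 − (1 − 0.0014)^500 = 50.4% (stated 50%).
- Upper bound with no events: 1 − 0.025^(1/500) = 0.735%, or 1 in 136 (stated below 0.74%, 1 in 136).

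All three reproduce. They concern one arm and do not use the between-group interval, for which the documents state no width.

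**Large-sample check.** With stratum shares w, risks p and mean risk m:
- Variance ratio, stratified to unstratified = Σ w p(1 − p) / [m(1 − m)].
- Half-width = 1.96 × √(2 × variance / 500).

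The inputs are assumptions: shares of 20/10/15/55% (CLD / CHD / neither below 29 weeks / neither 29 weeks or more) and SAE risks of 30/45/20/10%.
- m = 0.060 + 0.045 + 0.030 + 0.055 = 0.19.
- Unstratified variance: 0.19 × 0.81 = 0.1539.
- Within-stratum variance: 0.20 × 0.21 + 0.10 × 0.2475 + 0.15 × 0.16 + 0.55 × 0.09 = 0.14025.
- Ratio: 0.14025 / 0.1539 = 0.911.
- Half-widths: 1.96 × √(2 × 0.1539 / 500) = 4.86 points; 1.96 × √(2 × 0.14025 / 500) = 4.64 points.
- Width: √0.911 = 0.955, so 4.5% narrower. In sample size this is 1/0.911 = 1.10, about 10% more infants.
- Coverage of the unstratified interval: 2Φ(1.96/0.955) − 1, about 96.0%.

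With the same shares, risks of 20/25/15/10% give a variance ratio of 0.977 (√0.977 = 0.988, 1.2% narrower). Risks of 40/60/30/10% give 0.839 (√0.839 = 0.916, 8.4% narrower).

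**Simulation of the actual score intervals.** Miettinen and Nurminen intervals were computed unstratified and stratified over the eight cells with weights n1·n2/(n1 + n2). There were 500 infants per arm, no treatment effect and 800 trials per row. Assumed shares were 25/12/13/50% by condition and 80/20% by region.

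| Assumed event risk | Unstratified width (points) | Stratified width (points) | Ratio |
|---|---|---|---|
| 1% in all strata | 2.84 | 2.86 | 1.005 |
| Near 1%, two-fold differences | 2.80 | 2.83 | 1.010 |
| 5% in all strata | 5.54 | 5.54 | 1.000 |
| 30% in all strata | 11.35 | 11.35 | 1.000 |
| 20/30/15/10% (moderate) | 9.03 | 8.89 | 0.985 |
| 75/80/70/60% (moderate) | 11.60 | 11.44 | 0.986 |
| Same, one region at 0.7 times the risk | 11.92 | 11.62 | 0.975 |
| 30/50/15/10% (strong) | 10.02 | 9.46 | 0.944 |
| 40/70/15/10% (extreme) | 10.80 | 9.55 | 0.885 |

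Coverage of the unstratified interval ran from 0.950 to 0.976. The simulation error at 95% is √(0.95 × 0.05 / 800) = 0.8 points. In the rare-event row with two-fold differences both intervals covered about 97%, so the excess there does not come from the strata.

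**The case against.** The strongest reply is that this is a preference about efficiency. The unstratified method is stated explicitly and the same way in both sections. It introduces no bias and is at worst mildly conservative. The intervals are labelled descriptive, no margin or test depends on them, and Section 9.10 already looks at selected safety endpoints by stratum. All of this stands, and it is why the point is optional.

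The reply is also right that the benefit cannot be read from the documents. The only SAE percentages there (0.14%, 0.33%, 0.74%) are detectability limits, not expected rates. A reader might infer that the safety intervals are wider than they should be across the primary endpoints. The documents do not support that. It would need stratum rates that they do not give, and for rare endpoints such as the AESI the effect vanishes or reverses.

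Stratifying everything would also have a cost. At the 1% Tier 2 threshold there are about 5 events in 500 infants, spread over eight cells, so a blanket change would slightly widen those intervals.

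The descriptive label does not fully answer the point. Section 9.6.2 attaches it because many intervals are shown without multiplicity adjustment, which is no reason to leave the strata out. Subgroup summaries do not sharpen the overall comparison either.

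**Conclusion.** The mismatch is real: stratified randomization and an adjusted efficacy model, but an unstratified comparison for the primary objective, with no reason given. Its consequence is conditional and mostly small. For common events the stratified interval is about 1.5% to 2.5% narrower under moderate stratum differences and about 4% to 6% narrower under strong ones. Larger gains need extreme differences. There is no gain with equal risks and a loss of 0.5% to 1% for events near 1%. These sizes rest on assumed stratum shares and event risks and on no treatment effect in the simulations.

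A reader might go further and infer that the planned intervals are invalid or that a stated precision figure is wrong. Neither follows: the intervals hold their coverage, and the Section 9.9.2 figures do not use them. The point is a cheap improvement of optional severity.

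**What to change.** In Sections 9.1 and 9.6.2 and Table 7, name the common broad categories: any AE, nonserious AEs, any SAE, solicited injection-site and systemic AEs, and fever. For these, use the stratified Miettinen and Nurminen method with Cochran-Mantel-Haenszel weights, stratified by participant condition and by region where cells permit. State that region is collapsed first when cells are too sparse, in line with the provision in Section 9.6.1 for dropping a covariate. The rule should cover cells with infants but almost no events, as well as cells that are empty in one arm. Keep the unstratified interval for AESI and for AE terms near the 1% threshold, and report it as support for the listed categories. If the sponsor prefers to keep the present method, one sentence giving the reason and a stratified sensitivity analysis for any AE and any SAE would be enough.

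The cost is a wording change and a little extra analysis work. The strata are already recorded for randomization, and no new data are needed. The downside is no gain where strata do not differ, and a slightly wider interval if a listed category turns out to be rare.

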9.2 Responsibility for Analyses/In-house Blinding

The statistical analysis of the data obtained from this study will be the responsibility of the Clinical Biostatistics department of the Sponsor.

This study will be conducted as a double-blind study under in-house blinding procedures until the Sponsor study team, investigators, and participants are unblinded to the participant's treatment assignment at the RSV Season 1 Day 60 visit. Prior to unblinding each participant's treatment assignment, the participant's available safety data will be reviewed and locked.

The Clinical Biostatistics department will generate the randomized allocation schedule(s) for study treatment assignment. Randomization will be implemented using IRT.

9.3 Hypotheses/Estimation

Objectives of the study are stated in Section 3. There is no formal hypothesis testing in this study.

9.4 Analysis Endpoints

9.4.1 Efficacy Endpoints

The first secondary efficacy endpoint is the number of participants with RSV-associated MALRI (outpatient and inpatient) occurring from Days 1 through 150 post Dose 1 in the MK-1654 and palivizumab groups in RSV Season 1, as described in Section 4.2.1.1. RSV-associated outpatient and inpatient MALRI is defined as the following seen in an outpatient or inpatient clinical setting: cough or difficulty breathing; AND 1 or more of the following: wheezing, chest wall in-drawing/retractions, rales/crackles, hypoxemia, tachypnea, dehydration due to respiratory symptoms; AND RSV-positive RT-PCR NP sample.

The other secondary efficacy endpoint is the number of participants with RSV-associated hospitalization occurring from Days 1 through 150 post Dose 1 in the MK-1654 and palivizumab groups in RSV Season 1, defined as hospital admission for respiratory illness; AND RSV-positive RT-PCR NP sample.

The tertiary efficacy endpoints for this study are:

- Number of participants with RSV-associated MALRI occurring from Days 1 through 180 post Dose 1 in RSV Season 1 in the MK-1654 and palivizumab groups.
- Number of participants with RSV-associated hospitalization occurring from Days 1 through 180 post Dose 1 in RSV Season 1 in the MK-1654 and palivizumab groups.
- Number of participants with RSV-associated severe MALRI occurring from Days 1 through 150 post Dose 1 in RSV Season 1 in the MK-1654 and palivizumab groups.
- Number of participants with RSV-associated MALRI occurring from Days 1 through 180 postdose MK-1654 in RSV Season 2.
- Number of participants with RSV-associated hospitalization occurring from Days 1 through 180 postdose MK-1654 in RSV Season 2.
- Number of participants hospitalized with RSV-associated LRI from Days 1 through 150 post Dose 1 in RSV Season 1 in the MK-1654 and palivizumab groups.
- Number of participants hospitalized with RSV-associated LRI from Days 1 through 180 postdose MK-1654 in RSV Season 2.
- Number of participants with RSV-associated outpatient and inpatient MALRI excluding cases where other pathogens are found from Days 1 through 150 post Dose 1 in RSV Season 1 in the MK-1654 and palivizumab groups.
- Number of participants with physician-assessed wheezing from Days 1 through 150 post Dose 1 in RSV Season 1 in the MK-1654 and palivizumab groups.
- Number of participants with physician-assessed wheezing from Days 1 through 180 postdose MK-1654 in RSV Season 2.

